7.3.1.2 Paternal exposure

Male patients should refrain from fathering a child or donating sperm during the study and for 30 days after the last dose of CUDC-907.

Pregnancy of the patient’s partner is not considered to be an AE. However, the outcome of all pregnancies (spontaneous miscarriage, elective termination, ectopic pregnancy, normal birth, or congenital abnormality) occurring from the date of the first dose until 30 days after the last dose should, if possible, be followed up and documented.

7.4 EXPEDITED ADVERSE EVENT REPORTING CRITERIA TO THE PHARMACEUTICAL COLLABORATOR (CURIS)

All events listed below must be reported in the defined timelines to [contact].

The CCR Office of Regulatory Affairs will send all reports to the manufacturer as described below.

The collaborator has engaged Novella Clinical Inc. (“Novella”) for centralized safety reporting and pharmacovigilance for the CUDC-907 compound. Novella will be notified and provided information related to any, pregnancy, suspected unexpected serious adverse reaction (*SUSAR*) and serious adverse event (“SAE”) related to the Study Product, within twenty-four (24) hours of awareness of the event. Initial report may consist of limited information provided via email to [contact]. A full report will be provided within eleven (11) calendar days from the SAE event; such report shall be the same as submitted to the IRB and

FDA, including all SAE information from any Approved Sub-Investigator Site. Sub-investigators must report all SAEs to the Investigator so that the Investigator can meet his/her foregoing reporting obligations to the required regulatory agencies; such information shall be sent by fax to [name] or email [contact].

7.5 DATA AND SAFETY MONITORING PLAN

7.5.1 Principal Investigator/Research Team

The clinical research team will meet on a regular basis when patients are being actively treated on the trial to discuss each patient.

All data will be collected in a timely manner and reviewed by the principal investigator or a lead associate investigator. Adverse events will be reported as required above. The principal investigator will be responsible for revising the protocol as needed to maintain safety. Any safety concerns, new information that might affect either the ethical and or scientific conduct of the trial, or protocol deviations will be immediately reported to the IRB using iRIS and to the Sponsor.

The principal investigator will review adverse event and response data on each patient to ensure safety and data accuracy. The principal investigator will personally conduct or supervise the investigation and provide appropriate delegation of responsibilities to other members of the research staff.

7.5.2 Sponsor Monitoring Plan

As a sponsor for clinical trials, FDA regulations require the CCR to maintain a monitoring program. The CCR's program allows for confirmation of: study data, specifically data that could affect the interpretation of primary study endpoints; adherence to the protocol, regulations, and SOPs; and human subjects protection. This is done through independent verification of study data with source documentation focusing on:

- Informed consent process
- Eligibility confirmation
- Drug administration and accountability
- Adverse events monitoring
- Response assessment.

The monitoring program also extends to multi-site research when the CCR is the coordinating center.

This trial will be monitored by personnel employed by an NCI contractor. Monitors are qualified by training and experience to monitor the progress of clinical trials. Personnel monitoring this study will not be affiliated in any way with the trial conduct.

8 STATISTICAL CONSIDERATIONS

The primary objective of this trial is to determine the objective response rate of patients with locally advanced and or metastatic poorly differentiated and anaplastic thyroid cancer, and aggressive variants of differentiated thyroid cancer.

Patients will be enrolled into separate cohorts in order to estimate the response rates in each cohort: 1: Anaplastic thyroid cancer; 2: Poorly differentiated and aggressive variants of

differentiated thyroid cancer. Since there is no reliable information on expected clinical response rates in either cohort, each will be evaluated individually, with the primary objective in each cohort being to determine if using CUDC-907 would rule out a 5% response rate and target a rate of 25%. As such, in each cohort, the trial will be conducted using a Simon Minimax two-stage phase II trial design in order to rule out an unacceptably low partial (PR) + complete response (CR) rate of 5% ($p_0=0.05$) in favor of an improved response rate of 25% ($p_1=0.25$) [18]. With $\alpha=0.10$ (probability of accepting a poor treatment=0.10) and $\beta = 0.10$ (probability of rejecting a good treatment=0.10), this first stage will enroll 13 evaluable patients in a given cohort, and if 0 of the 13 have a clinical response, then no further patients will be accrued to that cohort. If 1 or more of the first 13 patients have a response in that cohort, then accrual would continue until a total of 20 evaluable patients have been treated in that cohort. As it may take up to several months to determine if a patient has experienced a response, a temporary pause in the accrual may be necessary to ensure that enrollment to the second stage is warranted. If there are 1 to 2 patients with a response out of 20 patients in a cohort, this would be an uninterestingly low response rate. If there were 3 or more of 20 (15%) who experienced a response, this would be sufficiently interesting to warrant further study in later trials with that cohort. Under the null hypothesis (5% response rate), the probability of early termination in either cohort is 51.3%.

In order to ensure that it remains safe to accrue patients, toxicity will be monitored in all patients. If at any time after 6 or more patients have been accrued in both cohorts combined, the cumulative fraction of patients with DLTs is 1/3 or greater, then no further patients will be enrolled on the trial.

Any secondary evaluations performed will be done in an exploratory fashion, with results presented without any formal adjustment for multiple comparisons.

It is anticipated that approximately 6 to 8 patients per year may enroll onto the trial. Thus, accrual of up to 40 total evaluable patients may be completed in approximately 5 to 7 years. In order to allow for a small number of in evaluable patients, the accrual ceiling will be set to 50 patients.

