3 STUDY IMPLEMENTATION

3.1 STUDY DESIGN

This will be an open label, phase II trial and patients will be given 60 mg of CUDC-907 orally once a day on a five days on and two days off schedule (5/2). One cycle will be 21 days. Patients may continue on treatment if there are no unacceptable adverse events (see Section 3.3) or disease progression on anatomic imaging. Response to treatment will be assessed after completing two cycles of treatment.

Patients will undergo ultrasound -guided biopsy of their tumor once before treatment if the site of disease is readily accessible without posing a significant risk to the patient. The tissue sample will be used for mutation profiling of common driver mutations and phosphoprotein profiling of commonly activated pathways in poorly differentiated and anaplastic thyroid cancer, and aggressive variants of differentiated thyroid cancer (**Table 1**).

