3.3.2 Dose Delays and Discontinuation of CUDC-907

In the event that any of the above criteria are not met, study drug dosing will be held until the retreatment criteria are met. Treatment may then resume at the full dose of CUDC-907, as long as none of the criteria in **Table 4** and/or **Table 5** are met. Beyond Cycle 1, subjects held for > 7 days may restart treatment after the subject has met the above criteria at the discretion of the Investigator. Beyond Cycle 2, subjects may have study drug held for up for 1 full cycle (21 days). If beyond 1 full cycle, then the subject will be taken off treatment per section **4.9.2**.

Subjects who experience a DLT-like event will be either discontinued from further study treatment or their dose will be reduced as outlined in **Table 3**. A DLT-like event will be defined as any of the following AEs occurring at any time:

- Non-hematological \geq Grade 3 AE, other than Grade 3 nausea or Grade 3 vomiting in subjects treated with less than optimal antiemetic therapy.
- An AE resulting in a dose delay of 21 days.
- Grade 4 neutropenia \geq 7 days, or \geq Grade 3 neutropenia with fever > 101.3°F (38.5°C) or \geq Grade 3 neutropenia with infection.
- Grade 4 thrombocytopenia \geq 7 days, or \geq Grade 3 thrombocytopenia and significant bleeding.

Table 3 CUDC-907 Dose Reduction Steps

Reduction Steps:	Schedule	Dose
Starting dose	5/2	60 mg
Dose Reductions	Schedule	Dose
First dose reduction	4/3	60 mg
Second dose reduction	5/2	30 mg
Final dose reduction	4/3	30 mg

4/3 = 4 days on, 3 days off; 5/2 = 5 days on, 2 days off

Dose Adjustments for CUDC-907 Hematologic and Non-hematologic Toxicity

The administration of HDAC and PI3K inhibitors has been associated with predictable bone marrow suppression that is typically transient and reversible.

The administration of HDAC and PI3K inhibitors has also been associated with hyperglycemia. This hyperglycemia does not generally result in severe metabolic complications and typically resolves with therapeutic intervention. The treatment goal for glycemic control is fasting plasma glucose < 160 mg/dL; while making every attempt to avoid hypoglycemia. Dose modifications of CUDC-907 are based on the severity of toxicities.

CUDC-907 dose adjustments for hematologic and non-hematologic toxicities are shown in **Table 4** and **Table 5**.

Table 4 CUDC-907 Dose Adjustments for Hematologic and Non-Hematologic Toxicities			

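### The toxicity rule waits for 6 patients, although 2 DLTs among the first 2 to 5 already settle closure, so 1 to 4 more patients may enrol after the outcome is fixed

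*Combined protocol and SAP*

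**What the plan says.** Section 8 states that "toxicity will be monitored in all patients" and gives one enrolment rule for safety. Its condition opens "If at any time after 6 or more patients have been accrued in both cohorts combined" and continues: "the cumulative fraction of patients with DLTs is 1/3 or greater, then no further patients will be enrolled on the trial". No operating characteristics are given for this rule. The only accrual pause that Section 8 describes concerns response at the end of stage 1.

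On timing, Section 8 says: "It is anticipated that approximately 6 to 8 patients per year may enroll onto the trial". It adds that "the accrual ceiling will be set to 50 patients". Section 3.1 says "One cycle will be 21 days". Section 8 does not define a DLT. The nearest definition is in Section 3.3.2: "A DLT-like event will be defined as any of the following AEs occurring at any time". That section governs dosing of the individual patient, not enrolment.

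Section 7.5.1 provides for regular team meetings about each patient, review of each patient's adverse events by the principal investigator, immediate reporting of safety concerns to the IRB and sponsor, and revision of the protocol where safety requires it. None of these carries a numeric trigger.

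**The concern.** A minimum number before a proportion is applied normally guards against closing a trial on too little information. That reason disappears once no later result can change the decision, which is the position here as soon as a second DLT occurs within the first 5 patients. From then until the sixth accrual, the rule permits new patients to start treatment although its own criterion is bound to be met.

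What is at stake is avoidable exposure of a small number of patients, not the validity of the response analysis.

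**Working it through.** **Plan's own figure.** Section 8 gives no figure for the toxicity rule. Its one stated probability, early termination of a cohort under the 5% null, reproduces as 0.95^13 = 0.513, against 51.3% stated. It is unaffected by this point.

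**Inputs.** Minimum accrual 6, boundary 1/3 with equality included, ceiling 50, and accrual of 6 to 8 a year (all Section 8); cycle of 21 days (Section 3.1). The true DLT rate p is an assumption. The lowest value used is 3/40 = 7.5%, the proportion of DLT-evaluable phase I patients with a DLT (Section 1.2). The values from 10% to 40% are illustrative.

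**Step 1: when closure is fixed.** At 6 patients the boundary is 2 DLTs, since 2/6 = 1/3. If the second DLT is in patient k, with k from 2 to 5, the count at patient 6 is at least 2 whatever follows. The rule then allows 6 − k further enrolments: 4, 3, 2 or 1.

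**Step 2: how likely this is.** P(at least 2 DLTs in 5) = 1 − (1−p)^5 − 5p(1−p)^4. At p = 0.075: 1 − 0.6772 − 0.2745 = 0.048.

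**Step 3: how many enrolments.** The second DLT falls in patient k with probability (k−1)p²(1−p)^(k−2). Expected avoidable enrolments are the sum over k = 2 to 5 of (6−k)(k−1)p²(1−p)^(k−2). At p = 0.075: 0.0225 + 0.0312 + 0.0289 + 0.0178 = 0.100. Dividing by 0.048 gives 2.1, the mean given that closure is fixed early.

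| Assumed DLT rate | Closure fixed before patient 6 | Expected avoidable enrolments | Mean given that it happens | DLT in both of first two (4 extra) |
|---|---|---|---|---|
| 7.5% | 4.8% | 0.10 | 2.1 | 0.6% |
| 10% | 8.1% | 0.17 | 2.1 | 1% |
| 20% | 26.3% | 0.59 | 2.2 | 4% |
| 30% | 47.2% | 1.13 | 2.4 | 9% |
| 40% | 66.3% | 1.70 | 2.6 | 16% |

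**Step 4: timing.** Accrual of 6 to 8 a year is one patient every 52/8 = 6.5 to 52/6 = 8.7 weeks, against a 3-week cycle. A DLT in the first cycle would often be known before the next patient enters. Four enrolments would take 4/8 to 4/6 of a year, or 6 to 8 months.

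**Step 5: effect of acting at the second DLT.** Running the rule patient by patient to 50, ignoring the response stop, the probability of closure is the same with and without the change. It is 13.0%, 44.5%, 79.9% and 97.3% at rates of 10%, 20%, 30% and 40%. Mean total enrolment goes from 44.4 to 44.2, 31.2 to 30.6, 17.4 to 16.3 and 9.4 to 7.7. These differences agree with the expected avoidable enrolments in the table.

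**The case against.** The strongest objection is that the problem may rarely arise. The DLT experience reported in the documents is low: 3 of 40 evaluable phase I patients across all schedules, none on the 5/2 schedule used here (Section 1.2) and none in the solid-tumour study (Section 11.1.12). At 7.5% the expected saving is a tenth of a patient. This stands, and it sets the low end of the range. It does not settle the matter, because the DLT-like definition in Section 3.3.2 is broad and has no time limit, so the rate in this trial could be higher.

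A reader might reach for the 43% with Grade 3 or worse events in phase I, or the 21% with Grade 3 events in the solid-tumour study, as likely DLT rates. The documents do not support that. Both are adverse-event rates. The 43% covers all phase I schedules, and its largest component is thrombocytopenia, which counts as DLT-like only if Grade 4 for at least 7 days, or Grade 3 or worse with significant bleeding. The solid-tumour study reported its 21% alongside no DLTs.

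Timing also limits the figures. Events can occur late, and some need 7 or 21 days to qualify, so a DLT may become known only after later patients have entered. This stands, and it makes the tabulated figures upper bounds at each rate.

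A reader might infer that even 5 DLTs in 5 patients would leave the trial running. That describes one sentence, not the whole oversight. Besides Section 7.5.1, Section 7.3 requires prompt reporting of serious events and Section 3.9.2 recognises an investigator decision to end the study. The narrower point remains that none of these obliges anyone to stop enrolment.

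Nor do the documents show that no patient with this disease had received the drug. Section 1.2 names tumour types for only 9 of the 15 solid-tumour subjects.

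**Conclusion.** The point holds as a cheap improvement in safety monitoring. Under the plain reading of Section 8, the written rule allows 1 to 4 enrolments after its own criterion has become certain to be met. The chance of reaching that position runs from about 5% at a DLT rate of 7.5% to 66% at 40%. Expected avoidable enrolments run from 0.1 to 1.7. The maximum of 4 requires a DLT in each of the first two patients, known before the third enrols.

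The calculation assumes independent patients with a common DLT rate, and that each DLT is known before the next accrual. Certainty of closure also requires the fraction to be checked when exactly 6 are accrued, which is the natural meaning of the text. If the first check were at 7, 2/7 = 28.6% would not trigger closure. Counting treated rather than accrued patients does not weaken the result, since 2 DLTs over 6 or fewer is still at least 1/3.

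It would go too far to say that the extra patients contribute nothing. They cannot alter the toxicity decision, but they would supply some response and safety data.

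**What to change.** Add one sentence to Section 8: if 2 patients have a DLT before 6 patients have been accrued in both cohorts combined, enrolment stops at that point, because the existing 1/3 boundary at 6 will necessarily be met. Leave the rule unchanged from 6 patients on. The same amendment could state whether DLT in Section 8 means the DLT-like event of Section 3.3.2, since the added sentence relies on the same undefined term.

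The cost is one sentence in an amendment and the loss of response and safety data from the few patients not enrolled. The sponsor's threshold and the probability of closure stay as they are. Alpha and power of the response design do not change either: the trial would close at 6 patients in any case, before either cohort could reach the 13 needed for stage 1.

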9 COLLABORATIVE AGREEMENTS

There is a CRADA agreement (03090) in place with Curis who is supporting this study.

10 HUMAN SUBJECTS PROTECTIONS

10.1 RATIONALE FOR SUBJECT SELECTION

Patients with metastatic or locally advanced poorly differentiated and anaplastic thyroid cancer will be selected for this study. To date, there is no information which suggests that differences in drug metabolism or disease response would be expected in any one patient group. Patient selection for this protocol will not be based on gender, race or ethnic background.

10.2 PARTICIPATION OF CHILDREN

Children will not be included on this protocol as poorly differentiated and anaplastic thyroid cancer is exceedingly rare in children.

10.3 PARTICIPATION OF SUBJECTS UNABLE TO GIVE CONSENT

Adults unable to give consent are excluded from enrolling in the protocol. However re-consent may be necessary and there is a possibility, though unlikely, that subjects could become decisionally impaired. For this reason and because there is a prospect of direct benefit from research participation (section 10.4), all subjects will be offered the opportunity to fill in their wishes for research and care, and assign a substitute decision maker on the “NIH Advance Directive for Health Care and Medical Research Participation” form so that another person can make decisions about their medical care in the event that they become incapacitated or cognitively impaired during the course of the study. Note: The PI or AI will contact the NIH Ability to Consent Assessment Team for evaluation. For those subjects that become incapacitated and do not have pre-determined substitute decision maker, the procedures described in NIHMEC Policy 87-4 for appointing a surrogate decision maker for adult subjects who are (a) decisionally impaired, and (b) who do not have a legal guardian or durable power of attorney, will be followed.

10.4 EVALUATION OF BENEFITS AND RISKS/DISCOMFORTS

Treatment with CUDC-907 may prove to be more effective treatment than systemic chemotherapy for locally advanced and metastatic poorly differentiated and anaplastic thyroid cancer. Patients with a long history of unresponsiveness to other treatment modalities may experience an actual therapeutic benefit. Risks include those associated with the agent, and standard imaging procedures for this disease entity. Care will be taken to minimize side effects, but they can be unpredictable in nature and severity. This study may involve risks to patients, which are currently unforeseeable. All patients will have laboratory tests to monitor for complications. If patients suffer any physical injury as a result of the participation of this study, immediate medical treatment is available at the Clinical Center, National Cancer Institute, Bethesda, Maryland. Although no compensation is available, any injury will be evaluated and treated in keeping with the benefits or care to which patients are entitled under applicable regulations.

10.4.1 Specimen Collection Risks

Risks also include those associated with specimen collection include pain, bleeding and the possibility of infection at the sampling site.

Risk of baseline biopsy: All care will be taken to minimize risks that may be incurred by tumor sampling. However, there are procedure-related risks (such as bleeding, infection and visceral injury) that will be explained fully during informed consent. If patients suffer any physical injury as a result of the biopsy, immediate medical treatment is available at the NIH’s Clinical Center in Bethesda, Maryland. Although no compensation is available, any injury will be fully evaluated and treated in keeping with the benefits or care to which patients are entitled under applicable regulations.

10.5 RISKS/BENEFITS ANALYSIS

Patients with locally advanced or metastatic poorly differentiated and anaplastic thyroid cancer have limited options available to them. CUDC-907 may provide anticancer activity in patients with advanced and metastatic poorly differentiated and anaplastic thyroid cancer. The potential

benefits outweigh the risks of treatment with CUDC-907. If this study demonstrates a tumor response to CUDC-907 a large, multicenter, trial using CUDC-907 in this population of patients will be considered.

The investigational nature and objectives of this trial, the procedures and treatments involved and their attendant risks and discomforts, potential benefits and potential alternative therapies will be carefully explained to the patient, and a signed informed consent document will be obtained by the PI, AI or clinical staff fellow.

10.6 CONSENT AND ASSENT PROCESS AND DOCUMENTATION

All patients who are being considered for this trial will undergo informed consent prior to being enrolled on the trial. The PI or associate investigator will perform the consenting process. Patients and family members when applicable will be asked to read the consent and will be encouraged to ask questions. It will be stated clearly that participation in the research study is voluntary and that participants can withdraw from the study without losing benefits they would otherwise be entitled to. Patients will be enrolled after the consent document has been signed. Separate consents will be obtained for any surgical procedures performed.

10.6.1 Reconsent via phone

The informed consent document will be sent to the subject. An explanation of the study will be provided over the telephone after the subject has had the opportunity to read the consent form. The subject will sign and date the informed consent. A witness to the subject signature will sign and date the consent.

The original informed consent document will be mailed, via the US Postal Service or FedEx, back to the consenting investigator who will sign and date the consent form with the date the consent was obtained via telephone.

A fully executed copy will be returned via mail for the subject's records.

The informed consent process will be documented on a progress note by the consenting investigator and a copy of the informed consent document and note will be kept in the subject's research record.

